6.1 ARQ 197 (tivantinib)

If using the recommended phase 2 dose (RP2D) of ARQ 197 (tivantinib) (360 mg BID), the following dose reductions for toxicity are suggested, in order: 240 mg BID, and 120 mg BID. See **Table 6-1** for a suggested dose modification plan for common toxicities.

Table 6-1: Recommended dose modification plan for ARQ 197 (tivantinib) for toxicity.

Event Grade (NCI CTC V4.02)	Action
Grade 1 or 2	Continue current dose level.
Grade 3 nonhematologic	If at least possibly related to ARQ 197 (tivantinib) and not amenable to an established, rapidly effective treatment*/**: discontinue ARQ 197 (tivantinib) until resolution to \leq Grade 2 Subsequent administration after discontinuation of ARQ 197 (tivantinib) should be at a dose that is decreased by one dose level for subsequent cycles, unless a second dose reduction is required. A maximum of 2 dose reductions is permitted per subject.
Grade 4 nonhematologic	If at least possibly related to ARQ 197 (tivantinib) and not amenable to an established, rapidly effective treatment*/**: discontinue ARQ 197 (tivantinib) until resolution to \leq Grade 2 Subsequent administration after discontinuation of ARQ 197 (tivantinib) should be at a dose that is decreased by one dose level for subsequent cycles, unless a second dose reduction is required. A maximum of 2 dose reductions is permitted per subject.
\geq Grade 3 neutropenia recovering within 5 days	Withhold ARQ 197 (tivantinib) If ANC recovers to $\geq 1.5 \times 10^9/L$ ($\geq 1500/mm^3$) within 5 days, resume treatment with ARQ 197 (tivantinib) at the same dose level.* If a second dose delay is required for the same event, then decrease ARQ 197 (tivantinib) dose by one dose level for subsequent cycles. For a third or fourth dose delay, decrease ARQ 197 (tivantinib) dose by one dose level. A maximum of 2 dose reductions is permitted per subject.
\geq Grade 3 neutropenia lasting >5 days or \geq Grade 3 febrile neutropenia	Withhold ARQ 197 (tivantinib) for up to 14 days. If ANC recovers to $\geq 1.5 \times 10^9/L$ ($\geq 1500/mm^3$) within 14 days, treatment with ARQ 197 (tivantinib) should resume at a dose that is decreased by one dose level for subsequent cycles. *** If a second or third dose delay is required for the same event, then again decrease ARQ 197 (tivantinib) dose from the current dose by one dose level for subsequent cycles. A maximum of 2 dose reductions is permitted per subject. If ANC does not recover to $\geq 1.5 \times 10^9/L$ ($\geq 1500/mm^3$) within 14 days after interrupting ARQ 197 (tivantinib), discontinue administration of ARQ 197 (tivantinib).
Platelet count $< 50 \times 10^9/L$ ($< 50,000/mm^3$)	Withhold ARQ 197 (tivantinib) for up to 14 days. If platelet count recovers to $\geq 100 \times 10^9/L$ ($\geq 100,000/mm^3$) within 14 days, resume treatment with ARQ 197 (tivantinib) at same dose level.* A maximum of 2 dose delays is permitted per subject. If a second dose delay is required for the same event, then decrease ARQ 197 (tivantinib) dose by one dose level for subsequent cycles. If platelet count does not recover to $\geq 100 \times 10^9/L$ ($\geq 100,000/mm^3$) within 14 days after interrupting ARQ 197 (tivantinib), discontinue ARQ 197 (tivantinib) administration.
Grade 4 thrombocytopenia	Discontinue administration of ARQ 197 (tivantinib).

* Treating Physician to assess relatedness and impact on patient health

** E.g. adverse events that are readily addressed with additional therapy – e.g. pain medication for increased pain, or insulin for elevated blood glucose levels

*** Patients requiring a delay of >2 weeks should go off protocol therapy.

6.2 Cetuximab

Cetuximab related toxicities	
Cetuximab Infusion Reaction	
 • Grade 1 (transient flushing or rash, drug fever <38oC): decrease the cetuximab infusion rate by 50% and monitor closely for any worsening. • Grade 2 (rash, flushing, urticaria, dyspnea, drug fever ≥38oC): stop the cetuximab infusion, administer appropriate therapy, and then restart the cetuximab infusion with a decrease in the infusion rate of 50% and monitor closely for any worsening. • Grade 1 or 2 Infusion Reaction manifesting only as a delayed drug fever (starting after the cetuximab infusion): maintain the cetuximab dose and infusion rate and consider administering acetaminophen or cyclooxygenase-2 inhibitors (at the dose and schedule of the investigator’s discretion) prior to the subsequent cetuximab infusion, if not otherwise contraindicated in the patient. • A grade 3 reaction consists of: symptomatic bronchospasm with or without urticaria, requiring parenteral medication(s); allergy-related edema/angioedema; hypotension. • A grade 4 reaction (anaphylaxis) is a life-threatening event characterized by rapid onset (often within minutes) of airway obstruction (bronchospasm, stridor, hoarseness), urticaria, and/or hypotension. • Treatment of a Grade 3 or 4 Infusion Reaction: Stop the cetuximab infusion immediately and disconnect infusion tubing from the patient. Administer epinephrine, bronchodilators, antihistamines, glucocorticoids, intravenous fluids, vasopressor agents, oxygen, etc, as medically indicated. • Following a grade 3 or 4 infusion reaction, the patient is to receive no further cetuximab treatment. In the event of a grade 1 or 2 infusion reaction, the cetuximab infusion rate should be permanently reduced by 50%. • Severe infusion reactions require the immediate interruption of cetuximab therapy and permanent discontinuation from further therapy. Appropriate medical therapies include epinephrine, corticosteroids, intravenous antihistamines, bronchodilators, and oxygen . Patients should be carefully observed until the complete resolution of all signs and symptoms.
Hypomagnesemia	
The incidence of hypomagnesemia (both overall and severe [NCI CTC grades 3 & 4]) is increased in patients receiving chemotherapy and cetuximab as compared with those receiving chemotherapy alone based on controlled clinical trials. Patients receiving cetuximab therapy should be monitored for hypomagnesemia. Magnesium repletion may be necessary based on clinical judgment.

Drug Fever	
In the event of isolated drug fever, the investigator must use clinical judgment to determine if the fever is related to the study drug or to an infectious etiology.
 
If a patient experiences isolated drug fever, for the next dose, pre treat with acetaminophen or non-steroidal anti-inflammatory agent (investigator discretion), repeat antipyretic dose 6 and 12 hours

	
after cetuximab infusion. The infusion rate will remain unchanged for future doses.
 
If a patient experiences recurrent isolated drug fever following pre-medication and post-dosing with an appropriate antipyretic, the infusion rate for subsequent dosing should be 50% of previous rate. If fever recurs following infusion rate change, the investigator should assess the patient's level of discomfort with the event and use clinical judgment to determine if the patient should receive further cetuximab.

Skin toxicities	
Patients developing dermatologic toxicities while receiving cetuximab should be monitored for the development of inflammatory or infectious sequelae, and appropriate treatment of these symptoms initiated. Dose modifications of any future cetuximab infusions should be instituted in case of severe (grade 3) acneform rash. Treatment with topical and/or oral antibiotics should be considered; topical corticosteroids are not recommended.
 
If a patient experiences severe acneform rash, cetuximab treatment adjustments should be made according to the following table. In patients with mild and moderate skin toxicity, treatment should continue without dose modification.
 
Management guidelines for treatment of skin toxicities are well established including antibiotics and topical therapies. An overview is provided in Appendix E.

Dose levels for cetuximab are as follows. Dose modifications are typically a result of skin toxicities, but at the discretion of the principal investigator other grade III/IV toxicities may also lead to a dose reduction if felt to be appropriate:

Cetuximab Dose Levels

	Every other week cetuximab dose
Starting dose	500 mg/m²
Dose Level -1	400 mg/m ²
Dose Level -2	250 mg/m ²

There will be no dose level reductions below a dose of 250 mg/m² every other week. An exception can be made if weekly (rather than every other week) dosing is felt to be beneficial, and may be attempted.

Management of Dermatologic Toxicity			
Grade	Cetuximab	Outcome	Cetuximab Dose Modification
Acneform Rash			
1st occurrence	Delay next infusion 1 to 2 weeks (per treating MD)	Improvement	Continue at 250 mg/m ²

		No Improvement	Discontinue cetuximab
2nd occurrence	Delay next infusion 1 to 2 weeks (per treating MD)	Improvement	Reduce Dose Level -1
		No Improvement	Discontinue cetuximab
3rd occurrence	Delay next infusion 1 to 2 weeks (per treating MD)	Improvement	Reduce to Dose Level -2
		No Improvement	Discontinue cetuximab
4th occurrence	Discontinue cetuximab		

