6. DOSING DELAYS/DOSE MODIFICATIONS

Dose Level	Tivantinib Dose
Starting Dose	360 mg, po, twice a day
-1	240 mg, twice a day
-2	120 mg, twice a day

Up to two dose reductions are acceptable. Persistent toxicities in spite of two dose reductions will result in discontinuation of therapy.

Event Name	Non-hematological toxicities	
Grade of Event	Management/Next Dose for ARQ 197 (tivantinib)	Management/Next Dose for Cetuximab
≤ Grade 1	Continue therapy	Continue therapy. See 6.2
Grade 2	Continue therapy	Continue therapy. See 6.2
Grade 3*	If at least possibly related to ARQ 197 (tivantinib) and not amenable to an established, rapidly effective treatment**: hold ARQ 197 (tivantinib) until resolution to ≤Grade 2	If at least possibly related to cetuximab and not amenable to an established, readily effective treatment**: hold cetuximab until resolution to ≤Grade 2. See 6.2
Grade 4*	If at least possibly related to ARQ 197 (tivantinib) and not amenable to an established, rapidly effective treatment**: hold ARQ 197 (tivantinib) until resolution to ≤Grade 2	If at least possibly related to cetuximab and not amenable to an established, readily effective treatment**: hold cetuximab until resolution to ≤Grade 2. See 6.2
* Treating Physician to assess relatedness and impact on patient health		
** E.g. adverse events that are readily addressed with additional therapy typically within 24 hours – e.g. pain medication for increased pain or insulin for increase blood glucose level.		
Patients requiring a delay of >2 weeks should go off protocol therapy. Patients requiring > two dose reductions should go off protocol therapy.		
Recommended management: For vomiting : antiemetics. For diarrhea : Loperamide antidiarrheal therapy. Dosage schedule: 4 mg first onset, followed by 2 mg with each loose motion until diarrhea-free for 12 hours (maximum dosage: 16 mg/24 hours). Adjunct anti-diarrheal therapy is permitted and should be recorded when used.		

Event Name	Hematological Toxicities***
------------	-----------------------------

Grade of Event	Management/Next Dose for ARQ 197 (tivantinib)	Management/Next Dose for Cetuximab
Grade 1	No change in dose	No change in dose
Grade 2	No change in dose	No change in dose

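### The first and second rows of the severe acneform rash table in Section 6.2 contradict each other: a patient already at the 250 mg/m² floor cannot be reduced again

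*Combined protocol and SAP*

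**What the plan says.** Both arms receive cetuximab at 500 mg/m² every two weeks (Sections 5 and 5.1.2). Section 6.2 lists the every-other-week levels as 500, 400 (Level -1) and 250 mg/m² (Level -2), and sets the limit: "There will be no dose level reductions below a dose of 250" mg/m². Weekly dosing is allowed as an optional exception.

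Under Skin toxicities, the same section states: "Dose modifications of any future cetuximab infusions should be instituted in case of severe (grade 3) acneform rash". It makes the table the operative rule: "If a patient experiences severe acneform rash, cetuximab treatment adjustments should be made according to the following table". Milder rash is treated differently: "In patients with mild and moderate skin toxicity, treatment should continue without dose modification".

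For each of the first three occurrences, the table delays the next infusion by one to two weeks and stops cetuximab if there is no improvement. If there is improvement, the instructions are:

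- first occurrence: "Continue at 250 mg/m"²
- second occurrence: "Reduce Dose Level -1"
- third occurrence: "Reduce to Dose Level -2"

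A fourth occurrence ends cetuximab.

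**The concern.** The first row already places the patient on the lowest permitted level, yet the next two rows step through Level -1 and Level -2 as if the patient were still on 500. The second row therefore has no dose that is both a reduction and allowed.

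What is at stake is patient safety and consistent dosing of the drug that causes the rash. Section 6.2 itself says that cetuximab dose modifications typically result from skin toxicity, so this is the main reduction rule for a drug given in both arms. At a second severe rash, one site could give 400, another could stay at 250 and a third could stop. At a first severe rash, a site that sees the conflict has to choose between 250 and 500, a two-fold difference.

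**Working it through.** The plan gives no derived figure to reproduce here. The check maps each row of the rash table to the dose-level table.

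**Inputs.** Start 500, Level -1 400, Level -2 and floor 250 mg/m², all every other week (Section 6.2). A cycle is 28 days (Section 5.1.2), so it holds two infusions. The patient is taken to be on 500 at the first severe rash and to improve after each delay.

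**Formula.** Change = (new dose − old dose) / old dose.

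| Reading | 1st occurrence | 2nd occurrence | 3rd occurrence | Fits the text? |
|---|---|---|---|---|
| A. As printed, second row taken as the named level | 500→250: −250/500 = −50% | 250→400: +150/250 = +60% | 400→250: −150/400 = −37.5% | No: a rise under an instruction to reduce |
| B. As printed, second row taken as one level lower | 500→250: −50% | below 250: no such level | – | No: breaches the floor |
| C. First row meant an unchanged 500 | 500→500: 0% | 500→400: −100/500 = −20% | 400→250: −37.5% | Falls properly, but the printed 250 must be replaced |
| D. First row meant 250 weekly | 2 × 250 = 500 per two weeks: 0% | 500→400 per two weeks: −20% | 400→250: −37.5% | Falls properly, but the word weekly must be added |

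Under reading A, the second-occurrence step per 28-day cycle is from 2 × 250 = 500 to 2 × 400 = 800 mg/m². The first-occurrence uncertainty between readings A and C is 2 × 250 = 500 against 2 × 500 = 1000 mg/m² per cycle.

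**Does another section settle it?**

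- The non-haematological table in Section 6 says "hold cetuximab until resolution to ≤Grade 2. See 6.2". It gives no restart dose and points back to the table in question.
- Appendix E refers to the modifications listed in the protocol and gives no dose.
- Sections 5 and 5.1.2 confirm only the starting dose.
- The protocol history lists no correction to this table.
- The Skin toxicities text in Section 6.2 calls for dose modification at grade 3 and reserves unmodified treatment for mild and moderate rash. That favours a cut at the first row and counts against readings C and D.
- The order of the second and third rows, and the verb in the first, favour no change at the first row. That counts against readings A and B.

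The text therefore points both ways on the first row. Readings A and B, which keep the printed 250 every other week, fail at the second row. Readings C and D work only after the text is changed.

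**The case against.** The strongest reply is that the table does not really instruct an increase. The second row's verb is to reduce, so giving 400 to a patient on 250 would disobey it, and a clinician would probably not do so. The rise also depends on the 250 in the first row being an intended every-other-week dose. It may be a misprint. The row speaks of continuing, and with 500 in its place the table uses each level once and then stops. The figure of 250 also matches the weekly dose in the single-agent cetuximab study described in Section 2.3, so it may be a carry-over from weekly dosing, though that is inference. Exposure is narrow too: the second row applies only after a delay and improvement, and Section 5.3 lets treatment end for unacceptable adverse events.

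Most of this stands. A reader might infer that the protocol directs a 60% escalation after a second severe rash. The documents do not support that. They support a self-contradictory instruction of which +60% is one reading.

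The reply does not supply a dose. A clinician who declines to escalate still has no valid level to give, and the misprint reading requires replacing a printed number against the grade 3 wording in the same section. The delay and the discretion to stop limit harm, but they do not tell a site what to infuse next.

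**Conclusion.** The concern holds as an internal inconsistency in a dosing-safety rule, and it should be fixed. As printed, the first and second rows cannot both be followed. At the second occurrence the choices are 400 mg/m² (+60% from 250, against the verb), a level below the floor that does not exist, or a dose the site chooses for itself. The intended first-occurrence dose is uncertain between 250 and 500 mg/m².

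This rests on the patient being on 500 mg/m² at the first severe rash, on improvement after each delay, and on the dose levels applying every other week as Section 6.2 labels them.

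Two further inferences are not supported. A reader might estimate how many patients would be affected, but the documents give neither a grade 3 acneform rash rate for this regimen nor the share with a second occurrence, so no count can be given. A reader might also suppose that the ambiguity biases the response comparison or costs power. The rule is the same in both arms, and nothing in the documents shows such an effect.

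**What to change.** Amend the table in Section 6.2 so that each occurrence states a dose in mg/m² and a schedule, in a sequence that never rises. The clinical team should choose the sequence:

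- **No cut at the first occurrence:** 500, 400, 250 mg/m² every other week, then stop at the fourth. The Skin toxicities text should then say that the delay alone is the first-occurrence adjustment.
- **Cut from the first occurrence:** 400, 250 mg/m² every other week, then stop at the third.
- **250 every other week kept in the first row:** the second row must say stay at 250 or stop, and the third row must be aligned.

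If 250 weekly was meant, the row should say so, and the later rows should state their schedule. Sites should then be notified.

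The cost is a wording amendment to one table, at most one sentence beside it, and a site notice. Sample size, endpoint and analysis do not change.

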7. ADVERSE EVENTS: LIST AND REPORTING REQUIREMENTS

Adverse event (AE) monitoring and reporting is a routine part of every clinical trial. The following list of AEs (Section 7.1) and the characteristics of an observed AE (Section 7.2) will determine whether the event requires expedited reporting (via CTEP-AERS) **in addition** to routine reporting.

7.1 Comprehensive Adverse Events and Potential Risks List(s) (CAEPRs)

7.1.1 CAEPRs for ARQ 197 (tivantinib) and Cetuximab

7.1.1.1 CAEPR for ARQ 197 (tivantinib, NSC 750832)

The Comprehensive Adverse Event and Potential Risks list (CAEPR) provides a single list of reported and/or potential adverse events (AE) associated with an agent using a uniform presentation of events by body system. In addition to the comprehensive list, a subset, the Specific Protocol Exceptions to Expedited Reporting (SPEER), appears in a separate column and is identified with bold and italicized text. This subset of AEs (SPEER) is a list of events that are protocol specific exceptions to expedited reporting to NCI via CTEP-AERS (except as noted below). Refer to the 'CTEP, NCI Guidelines: Adverse Event Reporting Requirements' http://ctep.cancer.gov/protocolDevelopment/electronic_applications/adverse_events.htm for further clarification. *Frequency is provided based on 756 patients.* Below is the CAEPR for ARQ 197 (tivantinib).

NOTE: Report AEs on the SPEER **ONLY IF** they exceed the grade noted in parentheses next to the AE in the SPEER. If this CAEPR is part of a combination protocol using multiple investigational agents and has an AE listed on different SPEERs, use the lower of the grades to determine if expedited reporting is required.

Version 2.2, February 19, 2016¹

Adverse Events with Possible Relationship to ARQ 197 (tivantinib) (CTCAE 4.0 Term) [n= 756]			Specific Protocol Exceptions to Expedited Reporting (SPEER)
Likely (>20%)	Less Likely (<=20%)	Rare but Serious (<3%)	
BLOOD AND LYMPHATIC SYSTEM DISORDERS			
	Anemia		Anemia (Gr 3)
CARDIAC DISORDERS			

Adverse Events with Possible Relationship to ARQ 197 (tivantinib) (CTCAE 4.0 Term) [n= 756]			Specific Protocol Exceptions to Expedited Reporting (SPEER)
Likely (>20%)	Less Likely (<=20%)	Rare but Serious (<3%)	
	Sinus bradycardia		
GASTROINTESTINAL DISORDERS			
	Diarrhea		Diarrhea (Gr 2)
	Nausea		Nausea (Gr 2)
	Vomiting		Vomiting (Gr 2)
GENERAL DISORDERS AND ADMINISTRATION SITE CONDITIONS			
Fatigue			Fatigue (Gr 2)
INVESTIGATIONS			
	Lymphocyte count decreased		
	Neutrophil count decreased		Neutrophil count decreased (Gr 4)
	White blood cell decreased		
METABOLISM AND NUTRITION DISORDERS			
	Anorexia		Anorexia (Gr 2)
SKIN AND SUBCUTANEOUS TISSUE DISORDERS			
	Alopecia		
		Palmar-plantar erythrodysesthesia syndrome	
	Rash maculo-papular		Rash maculo-papular (Gr 2)

¹This table will be updated as the toxicity profile of the agent is revised. Updates will be distributed to all Principal Investigators at the time of revision. The current version can be obtained by contacting [contact]. Your name, the name of the investigator, the protocol and the agent should be included in the e-mail.

²Infection includes all 75 sites of infection under the INFECTIONS AND INFESTATIONS SOC.

Adverse events reported on ARQ 197 (tivantinib) trials, but for which there is insufficient evidence to suggest that there was a reasonable possibility that ARQ 197 (tivantinib) caused the adverse event:

BLOOD AND LYMPHATIC SYSTEM DISORDERS - Febrile neutropenia; Lymph node pain
CARDIAC DISORDERS - Acute coronary syndrome; Atrial fibrillation; Cardiac arrest; Conduction disorder; Myocardial infarction; Paroxysmal atrial tachycardia
EYE DISORDERS - Dry eye; Eye disorders - Other (blindness unilateral)
GASTROINTESTINAL DISORDERS - Abdominal distension; Abdominal pain; Ascites; Constipation; Dry mouth; Duodenal ulcer; Dyspepsia; Flatulence; Gastrointestinal disorders - Other (eructation [belching]); Gastrointestinal disorders - Other (peritoneal hemorrhage); Mucositis oral; Oral pain; Small intestinal obstruction
GENERAL DISORDERS AND ADMINISTRATION SITE CONDITIONS - Chills; Edema limbs; Fever; Flu like symptoms; Gait disturbance; Malaise; Non-cardiac chest pain; Pain
HEPATOBIILIARY DISORDERS - Bile duct stenosis; Hepatic failure; Portal vein thrombosis
INFECTIONS AND INFESTATIONS - Infection²
INJURY, POISONING AND PROCEDURAL COMPLICATIONS - Fall; Fracture
INVESTIGATIONS - Alanine aminotransferase increased; Alkaline phosphatase increased; Aspartate aminotransferase increased; Blood bilirubin increased; Electrocardiogram QT corrected interval prolonged; GGT increased; INR increased; Investigations - Other (pancytopenia); Platelet count decreased; Weight loss

METABOLISM AND NUTRITION DISORDERS - Dehydration; Hypercalcemia; Hyperkalemia; Hyperuricemia; Hypoalbuminemia; Hypokalemia; Hypomagnesemia; Hyponatremia; Hypophosphatemia
MUSCULOSKELETAL AND CONNECTIVE TISSUE DISORDERS - Arthralgia; Back pain; Flank pain; Generalized muscle weakness; Musculoskeletal and connective tissue disorder - Other (muscle spasms); Neck pain; Pain in extremity
NEOPLASMS BENIGN, MALIGNANT AND UNSPECIFIED (INCL CYSTS AND POLYPS) - Treatment related secondary malignancy
NERVOUS SYSTEM DISORDERS - Dizziness; Dysgeusia; Headache; Intracranial hemorrhage; Nervous system disorders - Other (spinal cord compression); Peripheral motor neuropathy; Seizure; Stroke; Syncope; Transient ischemic attacks
PSYCHIATRIC DISORDERS - Anxiety; Confusion; Insomnia
RENAL AND URINARY DISORDERS - Acute kidney injury; Renal and urinary disorders - Other (hydronephrosis); Urinary retention; Urinary tract obstruction
REPRODUCTIVE SYSTEM AND BREAST DISORDERS - Pelvic pain
RESPIRATORY, THORACIC AND MEDIASTINAL DISORDERS - Allergic rhinitis; Bronchopulmonary hemorrhage; Bronchospasm; Cough; Dyspnea; Hypoxia; Pleural effusion; Pneumonitis; Pneumothorax; Respiratory failure; Respiratory, thoracic and mediastinal disorders - Other (oropharyngeal pain)
SKIN AND SUBCUTANEOUS TISSUE DISORDERS - Dry skin; Hyperhidrosis; Nail loss; Pruritus; Rash acneiform; Skin and subcutaneous tissue disorders - Other (skin fissures); Skin hyperpigmentation
VASCULAR DISORDERS - Hypertension; Hypotension; Thromboembolic event

Note: ARQ 197 (tivantinib) in combination with other agents could cause an exacerbation of any adverse event currently known to be caused by the other agent, or the combination may result in events never previously associated with either agent.

